### **Considerations for COVID-19 among Healthcare Workers in New Jersey**

As the densest state in America, New Jersey has been particularly hard-hit by coronavirus cases [29]. With 516,608 confirmed cases statewide as of January 8, 2021, those over age 65 have been greatly affected, comprising 16.8% of cases [30] and 79.8% of the state's 17,587 lab-confirmed deaths as of January 7, 2021 [30].

Healthcare workers – the subject of this study – have also been devastated by the virus. A study of NJ healthcare workers (HCW) early in the pandemic found that these employees were at greater risk for becoming infected than non-healthcare workers [31]. A 7.3% prevalence of infection was found among NJ healthcare workers versus 0.4% among non-healthcare workers [31]. Infections were particularly high among Black, Latino and “other” races [31]. The study acknowledged that further research is needed “to examine whether racial differences in COVID-19 among HCW may be related to their particular roles in the health care setting or are reflective of residence in communities that are more vulnerable to infection.”[31] More recent news attests to NJ team members continuing to fall ill, including over 100 at Hackensack Meridian Ocean Medical Center in December 2020 [32]. Statistical analysis in our study will examine demographic information such as race and occupational role.

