#### **4.2 Secondary and Exploratory Outcome Variables**

A separate analysis will be conducted to determine which post-covid symptom(s) are more impacted by omega-3 supplement. The Bi-weekly Symptoms and Quality of Life Post Covid-19 Survey (Appendix C) includes the four symptoms being measured (respiratory, fatigue, lack of taste, lack of smell). Therefore, this bi-weekly survey will be used for this efficacy analysis.

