  - Subjects in both arms will be tracked for 3 months (12 weeks). An interim analysis will be done for a sub-sample (the first 20 subjects) after three weeks of participation to determine if any arm should be adjusted or terminated.
  - Participants will continue to receive standard of care and follow up for any routine conditions being managed at HackensackUMC.
8. The final study activity will include the 2nd spot blood sample and a short survey (survey link emailed to subject via REDCap) to collect feasibility and acceptability data. The survey will take about 10 minutes to complete.

9. Subjects will then be mailed a \$40 gift card for completing the study.

10. Subjects will be informed of their omega-3 level after results are returned from the lab and the subject's participation in the study is complete

Any subject missing both daily doses 3 times a week for 3 weeks in a row will be removed from the study for non-compliance, and asked to dispose of any unused study supplement/placebo. This will be documented in a dedicated RedCap survey for anyone who discontinues study participation, either for non-compliance or of their own will.

Any subject who has another covid-19 infection during study participation may continue on the study. The RC will inform the subject of this if/when any subject reports a new covid infection.

[figure not shown]

Figure 1: Study Schema

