**Please select which week you stopped experiencing the symptoms described below.**

**If you never experienced this symptom, please select N/A**

	During the first two weeks since my covid-19 diagnosis	During the third week since my covid-19 diagnosis	During the fourth week since my covid-19 diagnosis	I still experience this symptom	N/A - I never experienced this symptom
Shortness of breath					
Cough					
Fatigue					
Lack of taste					
Lack of smell					
Other					

If you answered "Other," please specify/describe additional symptom #1: \_\_\_\_\_

If you answered "Other," please specify/describe additional symptom #2: \_\_\_\_\_

If you answered "Other," please specify/describe additional symptom #3: \_\_\_\_\_

Comment - Optional (please add here anything else you might want to share with us regarding any symptoms and/or your quality of life since your covid-19 diagnosis) \_\_\_\_\_

Please write-in your blood pressure, taken anytime in the last 2 weeks: \_\_\_\_\_

Source of blood pressure (BP) equipment and method:

- BP was taken by machine at home
- BP was taken by machine at a pharmacy
- BP was taken manually in medical office

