## Follow-up Survey - Covid Recovery Study

Please complete the survey below.

Thank you!

Were the instructions on how to take the pills clear?

Yes  
 No  
 Neutral / I don't know

If no, why not?

Did you not take the pills (skip one or more doses) at any time during 12-week study? (please refer to your pill log calendar)

No  
 Yes

If yes, how often did you not take the pills?

For how many days in a typical week did you take the pills?

Please include any comments about missed doses here:

Were the pills easy to take?

Yes  
 No  
 Neutral / I don't know

If no, why not?

Did taking the pills interfere with your daily activities somehow?

Yes  
 No  
 Neutral / I don't know

If yes, how?

How satisfied were you with your experience taking the pills?

Very satisfied  
 Satisfied  
 Neutral  
 Dissatisfied  
 Very dissatisfied

Are you willing to be contacted in the future about opportunities to participate in other research studies?

Yes  
 No

Confidential

Page 2

Since starting your participation in this study, has any doctor or other health care provider told you that you have any of the following illnesses? (please check all that apply)

- Diabetes or high blood sugar
- Hypertension or high blood pressure
- High cholesterol
- Stroke (ischemic or hemorrhage)
- Chronic lung disease such as asthma, emphysema, or chronic bronchitis
- Heart disease
- Cancer (other than skin cancer)
- Depression
- HIV/AIDS
- Other

If you answered "Other," please specify:

---

Please share anything else you would like us to know about your experience participating in this study:

---

During the 12-week study, did you receive the covid-19 vaccine?

Yes  
 No

If you did receive the covid-19 vaccine, did you experience any side effect(s)?

---

For how long did you experience side effect(s)? (please specify in # of days)

---

Is there anything else you would like to tell us that you might be important that we did not ask about?

---

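### Reinfected subjects may stay on study, but no structured survey item records or dates the reinfection, and the symptom grid does not say which covid-19 diagnosis it counts from

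*Combined protocol and SAP*

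**What the plan says.** Section 6.2 foresees reinfection and states that "Any subject who has another covid-19 infection during study participation may continue on the study". The only action attached is that "The RC will inform the subject of this if/when any subject reports a new covid infection". No recording step follows.

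Section 4.2 names respiratory symptoms, fatigue, loss of taste and loss of smell as the symptoms of interest, and says of Appendix C that "this bi-weekly survey will be used for this efficacy analysis". The Appendix C grid asks: "Please select which week you stopped experiencing the symptoms described below". Its first option is "During the first two weeks since my covid-19 diagnosis". Options for the third and fourth week follow, then one for a symptom still present and one for a symptom never experienced.

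Appendix A item 4 dates the qualifying PCR diagnosis. Appendix D asks "During the 12-week study, did you receive the covid-19 vaccine" and lists newly diagnosed illnesses. Covid-19 is not on that list, which ends with an open category for anything else.

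Section 17.1 calls the comparison of symptom recovery between arms, by chi-square or Fisher's exact test, the primary analysis. It does not define recovery or mention reinfection. Section 4.1, by contrast, makes feasibility and acceptability the primary endpoint.

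**The concern.** The symptoms used to judge efficacy are the ones that Section 10.0 treats as covid-19 symptoms, so a second infection can produce them afresh. A subject whose original symptom has cleared may then report it as present. A subject who entered with fatigue alone may acquire a cough that clears, which reads as a recovered cough. In either case the answer describes the new illness and not the course of long covid.

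The analyst would need to know who was reinfected and when, and the survey does not ask. The grid adds a second difficulty: after a new diagnosis its time origin has two readings, and subjects may differ in which they use. At stake are how far the symptom results can be interpreted and their use as proof of concept for the larger trial described in Section 2.0.

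**Working it through.** **1. Is a reinfection captured anywhere?** No structured item exists in Appendices A to D. Three other routes do exist:

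| Route | What it could show | What is lacking |
|---|---|---|
| Weekly coordinator calls (6.2), notes kept in REDCap as study data (17.3) | A reinfection mentioned in a call, placed to about a week | The only question set for these calls concerns bleeding (15.0); no covid-19 prompt |
| Adverse event records (19.1.1, 19.1.2) | A new infection meets the definition whether or not related to treatment; recording runs from first dose to 30 days after the last | Questions are to be non-leading; no onset date is named; no rule carries the record into the symptom analysis |
| Free text in Appendices C and D | Whatever the subject volunteers | Optional and unprompted; Appendix D comes once, at the end |

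Section 8.0 mentions results of two covid-19 tests, but Section 6.2 schedules none, so this cannot be counted as a route. Partial capture is therefore possible. Complete, dated capture is not provided for.

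**2. What does the grid record after a reinfection?** Take an invented subject who enters 14 weeks after the qualifying diagnosis with fatigue, is diagnosed again at the end of study week 4, and is free of fatigue during study week 7.

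- Counted from the qualifying diagnosis, fatigue stopped at about week 14 + 7 = 21. No option fits: the dated options end at week 4, the symptom is no longer present, and it was experienced.
- Counted from the new diagnosis, it stopped in week 7 - 4 = 3, and an option exists.

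The same history has no valid answer on one reading and a valid answer on the other.

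**3. Would naming the diagnosis be enough?** No. The inclusion list requires more than 12 weeks of symptoms, so the last dated option passed more than 12 - 4 = 8 weeks before entry. Even on the Study Summary's figure of 28 or more days since a positive test, 28/7 = 4 weeks, and every dated option has passed by entry. Resolution during the study cannot be dated for anyone, reinfected or not.

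**4. How large could the effect be?** The plan states no reinfection rate, recovery rate or power, so there is no figure to reproduce. What follows is illustration only. Assume that a fraction r of would-be recoverers in each arm is scored as not recovered because of a new infection. Each observed rate is the true rate times (1 - r), and so is the difference. With n = 50 per arm (Section 12.0), two-sided alpha 0.05 (the sidedness is assumed) and p̄ the mean of the two rates:

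power = Φ{ [(p2 - p1) - 1.96 √(2p̄(1 - p̄)/n)] / √([p1(1 - p1) + p2(1 - p2)]/n) }

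For r = 10% and assumed true rates of 30% and 50%: p1 = 0.27, p2 = 0.45, p̄ = 0.36. The two standard errors are √(2 × 0.36 × 0.64/50) = 0.0960 and √((0.1971 + 0.2475)/50) = 0.0943. Then (0.18 - 0.1882)/0.0943 = -0.087, and power is 46.6%.

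| r | Observed, true 30% v 50% | Difference (points) | Power | Power, true 30% v 60% | Power, true 40% v 60% |
|---|---|---|---|---|---|
| 0 | 30.0 v 50.0 | 20 | 53.3% | 86.6% | 51.6% |
| 5% | 28.5 v 47.5 | 19 | 49.9% | 83.2% | 47.7% |
| 10% | 27.0 v 45.0 | 18 | 46.6% | 79.4% | 43.9% |
| 20% | 24.0 v 40.0 | 16 | 40.2% | 71.1% | 37.0% |

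If outcome is read at one final survey, r is the share with new-infection symptoms at that time, not the share ever reinfected. At a constant infection rate with symptoms lasting d weeks, new infections over 12 weeks are about r × 12/d. For d of 2 to 4 weeks (assumed), r = 5% implies 15% to 30% of subjects reinfected and r = 10% implies 30% to 60%. For r = 20% the figure is 60% to 120%, so the last row is hard to credit unless symptoms last longer.

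The opposite error, a new symptom that clears and is read as recovery, is not quantified. If reinfection differs by arm, the direction of bias is unknown.

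**The case against.** The strongest reply is that the trial is not blind to reinfection. Subjects are called weekly, the investigator must ask about adverse events, a new infection qualifies as one, and surveys and call notes sit in REDCap under a common identifier. A reader might infer that new and persisting symptoms can never be told apart. The documents do not support that: these records could identify and roughly date some reinfections. What stands is that capture is unprompted and no rule brings it into the analysis.

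A reader might also infer that reinfection symptoms are counted against recovery. Recovery is undefined in Section 17.1, so one can say only that they may be. Fatigue also has a separate 14-day rating in Appendix C that does not depend on the diagnosis anchor. That rating helps with the anchor but not with the cause of the fatigue.

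Section 3.0 reports for New Jersey healthcare workers that "these employees were at greater risk for becoming infected than non-healthcare workers". It is tempting to read this as a high reinfection risk. The figures behind it (7.3% v 0.4%) are infection prevalences early in the pandemic. They do not speak to reinfection of previously infected staff, most of whom Section 10.0 expects to be vaccinated. Nor do the documents support a statement of how many more subjects a later trial would need, since they give no rate to work from.

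Finally, keeping reinfected subjects in a randomized, blinded comparison is a legitimate choice, and Section 17.1 says that the study is not powered for its analyses. Both points are right. They limit the importance of the gap but do not close it.

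**Conclusion.** The concern holds as a gap in data capture and in the analysis rules. Reinfected subjects may continue, no structured item records or dates the event, the grid's anchor is ambiguous after a second diagnosis, and no rule links the other records to the outcome. New acute symptoms may enter the recovery comparison and cannot be reliably separated from persisting ones.

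The size is unknown. If the misclassification is equal in both arms and in one direction, the difference shrinks in proportion to (1 - r). At r of 5% to 10%, power at 50 per arm falls by about 3 to 8 percentage points across the assumed recovery rates. Severity is minor to moderate: symptoms are a secondary outcome under Section 4.2, although Section 17.1 gives their comparison the name of primary analysis. The grid's fourth-week limit is a larger fault that exists without any reinfection, and it should be repaired in the same edit.

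**What to change.** - **Appendix C, new item:** *New positive covid-19 test since the last survey (or since enrolment, at the first survey)? Yes / No; if yes, date.*
- **Appendix C, grid:** refer to the infection dated in Appendix A item 4, and replace the time options so that resolution during the 12 weeks can be recorded, for example by study week or by date. Naming the infection alone does not achieve this. Subjects may still be unable to attribute an overlapping symptom, which is why the reinfection date is needed as well.
- **Section 17.1:** define recovery; keep every randomized subject in the main comparison whether reinfected or not; report reinfections by arm; add one sensitivity analysis that sets aside surveys completed after a reinfection date, and state which survey then supplies the outcome.

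The rule on continuing in the study is untouched. The cost is a few seconds per survey, one wording change, one extra analysis, and IRB approval of the revised survey under Section 20.1. The sensitivity analysis excludes data on the basis of a post-randomization event and may remove a subject's final outcome, so it can only be supportive. Reinfection dates not collected during the study may not be recoverable afterwards, which favours making the change early.

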## **7.0 Data and Specimen Banking**

### **7.1 Data or specimens for future use**

Each subject will have two blood specimens collected for analysis of omega-3 levels. Those specimens will not be banked for future use after this study.

Data collected from questionnaires will be stored on the HMH REDCap database on the HMH server. Data will be stored for six years after the end of the study. Access to the data will be restricted to the study staff.

### **7.2 Data to be stored or associated with each specimen**

For each subject who has the 2 blood specimens taken, only the test result will be stored – together with the other study data - for six years per HMH policy. As the consent form indicates, “Spot blood samples will not be used for future research. The samples will be destroyed by Omega Quant Labs approximately two weeks after analysis.”

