#### **6.2 Research Procedures**

For an overview of the study, please see figure 1 below.

1. Team members who email the study team at the address on the flyer will be sent an eligibility survey in REDCap to determine if study inclusion criteria are met.
2. Those who meet study inclusion criteria will then be sent the study consent form in REDCap, and encouraged to call or email the study team with questions.

3. If the patient expresses further interest in study participation, s/he will be consented via REDCap and then will be sent a link to the baseline survey in REDCap.
4. Upon consent, RC will assign ID# and enter the subject into REDCap (study data management system).
5. Subjects will be randomly assigned to receive 3 Omega-3 (EPA+DHA) mini-capsules twice daily (total of 2,100mg per day) for 12 weeks in the experimental intervention arm or three placebo mini-capsules twice daily for 12 weeks.
  - Study supplement or placebo are supplied at no cost to the subject and will be mailed to the subject's home.
  - Study subjects will receive two shipments over the course of study participation.
    - Package 1 upon enrollment
    - Package 2 at the end of week 4
  - Subjects will also receive, in these shipments, two spot blood sample tests for omega-3 levels, and directions indicating when to use the test kits.
6. All study subjects in each arm will be asked to give a spot sample (2 drops) of blood at baseline and again after 12 weeks (end of study participation). This will be done using OmegaQuant test kits that are mailed to the subject's home. The de-identified samples will be mailed by the subject in the provided envelope to OmegaQuant Lab, associated with University of South Dakota Medical Center, for analysis of omega-3 levels. These tests involve no cost to the subject. Subjects will be informed of their omega-3 level after results are returned from the lab and the subject's participation in the study is complete.
7. Monitoring of Subjects:
  - Subjects will be encouraged to call RC at any time with study questions. RC will also call each subject weekly to ensure procedures are being followed and answer any questions. The weekly "check-in call" will occur for 12 weeks.
  - Each subject will be checking their blood pressure. Subjects will report their blood pressure via REDCap in their bi-weekly survey. Reported adverse events will be documented.

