## **8.0 Sharing of Results with Subjects**

Individual-level data (the results of both COVID-19 tests and the omega-3 levels from the blood draw if applicable) will be shared with participants. The major findings of the study and aggregate data, will be shared with participants after the study has concluded.

1) Unblinding will occur when a subject drops out of the study due to an adverse event. The subject will be informed of their study arm assignment via email so that they can better understand any possible adverse reaction to the study medication.

2) Subjects who complete the study will be unblinded and informed of their study arm assignment via email after the study team has seen their data (descriptive statistics generated by RedCap). This will be done within 4 weeks of each subject finishing the study.

The study coordinator will inform each subject when they finish study participation, to expect an email advising which study arm they were in.

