## **19.2 Data Safety Monitoring**

The Hackensack Meridian Health Data and Safety Monitoring Board (DSMB) will be responsible for the data and safety monitoring of this trial. As this study is an investigator initiated feasibility study utilizing a non-FDA approved supplement for which the PI holds the IND it is considered a moderate risk study which requires real-time monitoring by the PI and study team and reviewed monthly by the HMH DSMB.

The Principal Investigator and the Co-Investigators will review the data including safety monitoring at their weekly institution-based meetings and on monthly teleconferences. All Severe Adverse Events (SAEs) are required to be reported to the IRB. Based on SAEs, the IRB retains the authority to suspend further accrual pending more detailed reporting and/or modifications to further reduce risk and maximize the safety of participants. Progress on the trial will be reviewed by the HMH DSMB monthly from the time the first participant is enrolled on the study. Results of the DSMB meetings will be forwarded to the IRB with recommendations regarding need for study closure. DSMB recommendations should be based not only on results for the trial being monitored as well as on data available to the DSMB from other studies. It is the responsibility of the PI to ensure that the DSMB is kept apprised of non-confidential results from related studies that become available. It is the responsibility of the DSMB to determine the extent to which this information is relevant to its decisions related to the specific trial being monitored. A written copy of the DSMB recommendations will be given to the trial PI and the IRB. If the DSMB recommends a study change for participant safety or efficacy reasons, the trial PI must act to implement the change as expeditiously as possible. If a recommendation is made to change a trial for reasons other than patient safety or efficacy, the DSMB will provide an adequate rationale for its decision. Authority to close a trial for safety reasons lies with the IRB, with the above described input from DSMB.

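### Week-12 omega-3 levels are released subject by subject and not masked from study staff, giving a second route to probable arm beside the arm e-mail in section 8.0, while others are still being enrolled and followed

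*Combined protocol and SAP*

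**What the plan says.** The trial is described as double blind (sections 1.0 and 6.1), and Appendix E specifies one label for both products so that the blind is kept. Section 6.2 item 6 has the omega-3 level measured twice in both arms: "All study subjects in each arm will be asked to give a spot sample (2 drops) of blood at baseline and again after 12 weeks". On release, items 6 and 10 say: "Subjects will be informed of their omega-3 level after results are returned from the lab and the subject's participation in the study is complete". The trigger is that subject's own completion, not the end of the trial. Section 8.0 repeats that individual omega-3 levels are shared.

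On storage, section 7.2 says "only the test result will be stored", and places that result with the rest of the study data. On access, section 7.1 says "Access to the data will be restricted to the study staff". Section 19.2 adds: "The Principal Investigator and the Co-Investigators will review the data including safety monitoring at their weekly institution-based meetings". Samples reach the laboratory de-identified (sections 6.2 and 17.3). That protects confidentiality, but it does not keep results from the trial team.

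Section 8.0 also plans a direct disclosure: "Subjects who complete the study will be unblinded and informed of their study arm assignment via email after the study team has seen their data", within 4 weeks of each subject finishing. The only planned interim look is in section 6.2 item 7, on the first 20 subjects after three weeks of participation, before any week-12 level exists.

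**The concern.** The active arm takes EPA and DHA and the control arm takes soybean oil (section 6.1). The laboratory measures omega-3, so a rise from baseline to week 12 is a marker of the assigned product. If results arrive one at a time in data open to staff, completers can be sorted by change in level and their symptom answers compared by probable arm while the trial is still running.

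Three things are at stake. The first is an unplanned comparative look in a trial whose section 17.1 names symptom recovery by arm as the primary analysis, leaves the choice of test open and allows further exploratory analyses. The second is the judgement of staff who call the remaining subjects weekly (section 6.2), assess adverse events, and decide whether a subject with an adverse event continues (section 15.0). The third is the completer's own later data: the end of the 30-day adverse-event window (section 19.1.2) and the 6-month call (section 19.3).

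The laboratory route needs naming separately because delaying only the arm e-mail would leave it open.

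**Working it through.** The plan states no figure on this point, so there is none to reproduce. Two quantities can be checked.

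**1. How well the level could identify the arm.** The documents give no expected change, SD or placebo change; supplier text in Appendix E says only that levels improve with months of use. Assume normal changes with equal SD in both arms, 1:1 allocation, a cut at the midpoint, and means d SDs apart. The share classified correctly is p = Φ(d/2):

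- d = 1: Φ(0.5) = 69%
- d = 2: Φ(1.0) = 84%
- d = 3: Φ(1.5) = 93%

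Guessing gives 50%. If symptoms are unrelated to the level within an arm, the difference seen between the two guessed groups is (2p − 1) times the true one: 0.38, 0.68 or 0.87 of it.

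**2. How much of the trial is still ahead when results arrive.** Each subject is on study for 12 weeks (section 9.0). Enrolment is 6 months in the text of section 9.0, but its table marks 5 months (months 4 to 8), so take E = 22 or 26 weeks. Assumptions: uniform accrual, no dropout, and a laboratory lag L of 1 to 4 weeks.

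- First result back: week 12 + L
- Share randomised after it: (E − 12 − L)/E
- Share of on-study subject-weeks after it: (E − L − 6)/E
- 20% of results back: week 12 + L + 0.2E, after which (0.8E − 12 − L)/E are still to be randomised

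| E | L | First result (week) | Randomised after | Subject-weeks after | 20% back (week) | Randomised after that |
|---|---|---|---|---|---|---|
| 22 | 1 | 13 | 9/22 = 41% | 15/22 = 68% | 17.4 | 4.6/22 = 21% |
| 22 | 4 | 16 | 6/22 = 27% | 12/22 = 55% | 20.4 | 1.6/22 = 7% |
| 26 | 1 | 13 | 13/26 = 50% | 19/26 = 73% | 18.2 | 7.8/26 = 30% |
| 26 | 4 | 16 | 10/26 = 38% | 16/26 = 62% | 21.2 | 4.8/26 = 18% |

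The first-result columns show when exposure begins. One result says nothing about outcomes by arm, so the 20% columns are the fairer gauge of when a comparison becomes possible. At that point the share of on-study subject-weeks still ahead is 0.8 − (L + 6)/E, which runs from 35% (E = 22, L = 4) to 53% (E = 26, L = 1).

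**Timing within a subject.** The second sample and the feasibility survey form the final study activity (section 6.2 item 8), and the level is released only after participation ends. It therefore follows that subject's 12-week answers. With a lag of 7 to 28 days it comes before the 30-day adverse-event window closes and well before the 6-month call.

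**The case against.** The strongest objection is that section 8.0 already discloses each completer's arm outright, so a probabilistic proxy adds little to the plan as written. That is right about relative size: the arm e-mail is the larger breach, and withholding levels alone would achieve little. It does not remove the point, because a sponsor who repaired only the e-mail would leave this route open.

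Staff sight of the levels is also inferred. The access sentence in section 7.1 follows one on questionnaire data, section 17.3 describes the data as survey responses and call notes, and section 19.2 does not mention omega-3. The inference is strong, since section 7.2 puts the results with the other study data and no firewall is described, but it is not an explicit statement.

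The bias path is narrower than it may look. Subjects still on study have only a baseline value, which cannot show their arm. Symptoms are self-reported, not rated by staff. Closing the study lies with the IRB, with DSMB input, not with the callers. The 6-month call has no stated endpoint. All of this stands and limits the likely harm.

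A reader might infer that the laboratory value gives away the arm, or that a subject's own symptom scores are contaminated. The documents support neither: they give no separation between arms, and the result comes after the 12-week surveys.

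**Conclusion.** The point holds as a gap in blinding that should be closed together with section 8.0. Following the plan as written releases a marker of probable arm, subject by subject and without masking, while enrolment and follow-up continue. With the arm e-mail, it allows an unplanned look at symptoms by arm and exposes staff who make later calls and adverse-event judgements, as well as each completer's late adverse-event reports and 6-month call.

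The overlap follows from the plan's own timeline under either enrolment length. Its size rests on uniform accrual and the assumed laboratory lag: 27% to 50% of subjects are randomised after the first result, and about 7% to 30% after a fifth of results. The accuracy figures of 69% to 93% are illustrations, not estimates. That the study is a feasibility trial without a power calculation lowers the stakes but does not remove them, because section 17.1 still makes a symptom comparison by arm the primary analysis. No sample size, alpha or power figure changes.

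**What to change.** Have the laboratory hold all omega-3 results, or send them to a file closed to study staff, until the last subject completes 12 weeks and the data are locked. Hold the routine arm e-mail to completers in section 8.0 to the same point. Then merge the results by study ID and report level and arm to subjects together. This point asks for no change to the separate provision in section 8.0 for subjects who drop out because of an adverse event.

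Amend section 6.2 items 6 and 10, section 7.2, section 8.0 and the consent wording in one step; changing only the laboratory sections would leave the larger route open. The 5- and 6-month enrolment periods in section 9.0 should be reconciled at the same time.

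The cost is protocol and consent text and one data-transfer instruction to the laboratory. The downside is that early completers wait some months for their level and arm.
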